## Research Protocol Guidelines (continued)

Clinical Assessments	Baseline	1 mo +/- 5d	3mo +/- 5d	6mo +/- 5d
Modified CDASI	X	X	X	X
aCAT	X	X	X	X
PGA (VAS scoring)	X	X	X	X
PGA (Likert scoring)	X	X	X	X
Global Patient Score (by pt)	X	X	X	X
Global Itch Score (by pt)	X	X	X	X
DLQI	X	X	X	X
MMT-8	X	X	X	X
MDAAT	X	X	X	X

Length of each test/procedure:

Modified CDASI: 5 min

aCAT: 5-10 min

PGA (VAS scoring): < 1 minute

PGA (Likert scoring): < 1 minute

Global Patient Score: < 1 min

Global Itch Score: < 1 min

DLQI: 5 min

MMT-8: 5 min

MDAAT: 15-30 min (depending on severity of disease)

\*\*see references above associated with each individual test for details concerning validity and reliability

### **Study End Points**

#### **1. Primary end-points:**

Statistically significant improvement in cutaneous manifestations of dermatomyositis based on changes in **modified CDASI** score, **CAT** score, and **Physician's Global Assessment (overall, activity, damage)** scores at end of study vs. baseline.

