### **Sample**

Our sample will include approximately 10-15 patients with refractory cutaneous symptoms related to either classic dermatomyositis, juvenile dermatomyositis, or amyopathic dermatomyositis. This sample size was chosen to ensure adequate power to detect 50% decreases in the mean total and activity scores of the modified CDASI, and 75% decreases in the mean damage scores. This is not affected by the baseline modified CDASI score (though the % change and coefficient of variation will change based on this level).

Our inclusion/exclusion criteria are as follows:

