## **Research Procedures**

- 1) Upon enrollment patients will undergo a thorough history (including assessing time of diagnosis), review of systems, and a complete physical examination.
- 2) A detailed examination of the skin and mucous membranes will be performed, noting for presence/absence of the following: scalp erythema and atrophy, heliotrope rash, typical erythema and atrophy of sun-exposed areas on the neck, upper chest and upper back (shawl sign), erythema +/- scaling of the elbows and/or knees (Gottron's sign), gottron's papules, periungual erythema, ragged cuticles, proximal nailfold capillary loops, palmar scaling and hyperkeratosis (mechanic's hands), a rash involving the hips (holster sign), oral ulcerations, cutaneous ulcerations, purpura.
- 3) Objective cutaneous dermatomyositis scoring by the primary investigator using the **modified Cutaneous Dermatomyositis Disease Area and Severity Index** (CDASI) score and **Abbreviated Cutaneous Assessment Tool** (aCAT) will be performed at each visit ([8-13](#)).
- 4) Objective general cutaneous disease scoring by the primary investigator using the **Physician Global Activity** for (a) **overall skin** (b) **skin activity** (c) **skin damage** will be performed at each visit (each assessed using both VAS-0-10 visual analog scale and Likert scale- 0-4 for each) ([9](#)).
- 5) Objective scoring tools to be completed by the patient at each visit will include: **Patient Global Assessment (Skin) Score** (0-10 visual analog scale), **Patient Global (Itch) Score** (0-10 visual analog scale), and the **Dermatology Life Quality Index** (validated quality of life assessment) ([8-12](#)).
- 6) Photographs of all cutaneous lesions will be performed at baseline and at each follow-up visit.
- 7) Evaluation for current presence of myositis will be performed using the **Manual Muscle Testing 8 (MMT-8)** scoring tool by the primary investigator, as well as with serologic studies below ([11, 12](#)).
- 8) Completion of the **Myositis Disease Activity Assessment Tool** (MDAAT) by the primary investigator to assess disease activity of extramuscular organ systems ([12](#)).
- 9) Serologic studies at baseline will include an AM cortisol level, CBC w/ diff, CMP, CK, aldolase, LDH, comprehensive myositis panel (ARUP labs), C3, C4, and HbA1c. The above serologic studies (except for the comprehensive myositis panel) will be repeated at the final visit.

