#### **2. Secondary end-points:**

a) Statistically significant change in **MDAAT** Score and **MMT-8** score

---

Protocol Version Date 7/30/14

- b) Statistically significant change in **Global Patient Score**, **Global Itch Score**, and/or the **Dermatology Life Quality Index scores** between baseline and 6 months.
- c) Safety and tolerability of H.P. Acthar gel based on frequency and types of adverse effects.
- d) median/mean change in glucocorticoid dose from initiation to completion of study.
- e) median/mean change in dose of systemic steroid-sparing immunosuppressive agents from initiation to completion of study.
- f) median/mean change in HbA1c

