### **Statistical Methods**

Patient and disease characteristics will be summarized using means, standard deviations, medians and other percentiles of interest for continuous measures and frequencies and percentages for categorical factors. Changes in scoring tool measures from baseline to six months will be calculated and compared using paired t-tests. If necessary, transformations of the data will be performed prior to analysis to meet distributional assumptions. If proper transformations cannot be found, then nonparametric Wilcoxon

signed rank tests will be performed. To assess trends scores over time, linear mixed effect models will be fit and estimates of the average change per month will be calculated. Analysis will be performed using SAS software (The SAS Institute; Cary, NC). A significance level of 0.05 will be assumed for all tests.

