## **Sample Size Considerations**

The primary assessment tool will be the CDASI. Scores for the modified CDASI range from 0 to 100 for activity, 0 to 32 for damage, and 0 to 132 for the total score. In the paper by Yassaee (2010), investigators found a mean (SD) activity score of 17.83 (10.14), a mean (SD) damage score of 2.27 (2.73), and a mean (SD) total score of 20.10 (10.25). Given the apparent skewed distributions for these scores, a log-normal distribution for the scores was assumed. In these distributions, a coefficient of variation (CV = SD/Mean) of 0.6 appears appropriate for activity and total scores, while a CV of 1.25 was assumed for comparisons of total score. The required sample size for each scale to achieve 80% power to detect 25%, 50%, and 75% decreases in CDASI scores, based on the assumptions above, and assuming use of two-sided paired t-tests on log-transformed values. These calculations further assume that a small positive correlation ( $r=0.25$ ) between baseline and 6-month scores within person, and use of a 0.05 significance level. Note that since Activity and Total CDASI scores assume the same CV, sample size requirements are identical. Under these assumptions, 10 patients are needed to detect a 50% decrease in the mean CDASI activity score or CDASI total score with 80% power. This sample size would allow adequate power to detect decreases of at least 70% in the mean damage score. Eight patients would be required to detect a 75% decrease in the mean damage score.

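### Five primary items have no rule for which must succeed, while the sample size section rests on CDASI alone: the two sections need reconciling and one score naming

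*Combined protocol and SAP*

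**What the plan says.** - **Primary end-points.** Success is "Statistically significant improvement in cutaneous manifestations of dermatomyositis based on changes in" the modified CDASI, the CAT and the Physician's Global scores for overall, activity and damage, at end of study against baseline. The items are joined by *and*. No sentence says how many must be significant.
- **Secondary end-points.** Item (a) joins MDAAT and MMT-8 with *and*. Item (b) lists two patient scores "and/or the Dermatology Life Quality Index scores between baseline and 6 months".
- **Statistical Methods.** Changes to six months are compared by paired t-tests, or by signed rank tests if no transformation works. "A significance level of 0.05 will be assumed for all tests". No hierarchy or adjustment is given.
- **Sample Size Considerations.** "The primary assessment tool will be the CDASI". Activity, damage and total scores are described, and "10 patients are needed to detect a 50% decrease in the mean CDASI activity score or CDASI total score with 80% power". CAT and Physician's Global get no power calculation.
- **Sample.** "Our sample will include approximately 10-15 patients with refractory cutaneous symptoms", a size meant to give adequate "power to detect 50% decreases in the mean total and activity scores of the modified CDASI, and 75% decreases in the mean damage scores".
- **Research Procedures.** The three Physician's Global items are "each assessed using both VAS-0-10 visual analog scale and Likert scale- 0-4 for each". The primary investigator does the CDASI, aCAT and Physician's Global scoring.

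**The concern.** A primary objective built on several tests needs a stated success rule, because the rule sets both the error rate and the power. If one significant item is enough, there are several chances of a false success. If every item must be significant, false success becomes rarer, but so does true success, and a sample size worked out for one score no longer applies. This plan states neither rule, and its sample size section points to a third reading in which CDASI alone decides.

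With nothing fixed in writing, the reading could be settled after the results are known. That matters more here than in a blinded trial, since the study is open-label, the primary investigator does the scoring, and the same investigator has access to the data.

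**Working it through.** **1. Reproducing the plan's figures.** Inputs from Sample Size Considerations: log-normal scores, CV 0.6 for activity and total, correlation 0.25 between baseline and 6 months, two-sided 0.05. The second CV, 1.25, is printed for total score. It is read here as the damage CV, because 2.73/2.27 = 1.20 and because only that reading reproduces the damage figures.

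SD of the log change = √[2 × ln(1 + CV²) × (1 − 0.25)]; effect = −ln(1 − fall); power from the noncentral t with n − 1 degrees of freedom.

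- Activity or total, 50% fall: SD = √(1.5 × ln 1.36) = 0.679; effect = ln 2 = 0.693; ratio 1.02. Power is 81.9% at n = 10 and 95.6% at n = 15. Ten is the smallest n reaching 80%, as stated.
- Damage, 75% fall: SD = √(1.5 × ln 2.5625) = 1.188; effect = ln 4 = 1.386; ratio 1.17. Power is 80.7% at n = 8, as stated, and 90.6% at n = 10.

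The single-score figures are therefore sound.

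**2. If any one item suffices.** A two-sided 0.05 test gives a false improvement 2.5% of the time. For five tests the ceiling is 5 × 2.5% = 12.5%, and under independence the chance is 1 − 0.975⁵ = 11.9%. The documents do not give the correlation between items, so it was varied (simulated t-tests, equal correlations, n = 10):

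| Assumed correlation | At least one false improvement in five |
|---|---|
| 0 | 12.0% |
| 0.5 | 9.5% |
| 0.8 | 6.9% |
| 0.9 | 5.3% |
| 0.95 | 4.4% |

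Results at n = 15 are within about half a percentage point.

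For the three CDASI scores, total = activity + damage, so the published SDs imply a correlation between activity and damage of (10.25² − 10.14² − 2.73²)/(2 × 10.14 × 2.73) = −0.09. That describes scores at one time, not changes, so 0.3 and 0.6 were also tried. The chance that at least one of the three shows a false improvement at n = 10 is 5.6%, 5.2% and 4.7% respectively.

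**3. If all must succeed.** For the three CDASI scores at the plan's own targets (50% fall in activity and total, 75% in damage), with the same correlations, joint power is about 72% to 77% at n = 10 and 93% to 94% at n = 15.

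For five items the plan gives no effect for CAT or Physician's Global. If each has the CDASI activity effect:

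| Assumed correlation | Power, n = 10 | Power, n = 15 |
|---|---|---|
| 0 | 37% (0.819⁵ = 0.37) | 80% |
| 0.5 | 52% | 85% |
| 0.8 | 65% | 89% |
| 0.95 | 74% | 93% |

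If the other four items have standardised effects 1.5 times as large, power at n = 10 is 80% to 82% for correlations of 0.5 to 0.9.

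**The case against.** The best defence is that the plan already has a lead measure: the sample size section names CDASI as the primary tool. This narrows the question but does not close it. The statement conflicts with the five-item list, does not say that CDASI alone decides success, and leaves three CDASI scores open, with activity and total offered as alternatives.

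A second defence is that *and* means all, which would involve no inflation. The contrast with *and/or* among the secondary end-points does lean that way. It is an inference from a conjunction, though, and the 10-patient calculation is not for a joint criterion.

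Two stronger readings are tempting, and the documents support neither.

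- A reader might infer that the plan carries a false-improvement rate of 15% or more. For five tests that is impossible, since the ceiling is 12.5%. A higher figure needs the CDASI scores and the VAS and Likert versions all counted separately, up to ten scores (3 + 1 + 6; 1 − 0.975¹⁰ = 22.4% if independent, less if correlated). The primary end-point refers to CDASI as a single score and mentions neither scale, so that count is a possible expansion and not what the plan states.
- A reader might infer that an all-items rule is underpowered outright. For five items that depends on how CAT and Physician's Global respond, which the plan does not say. Power is near 80% at n = 10 if they respond clearly better than CDASI, and 80% or more at n = 15, within planned enrolment.

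**Conclusion.** The gap is real and rests on the text alone: there are five primary items, no success rule, 0.05 for every test, and a sample size section that relies on CDASI without choosing its score. Its numerical consequences are conditional.

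- **Any of five items:** false improvement about 4% to 12%, against 2.5% for one test, depending on the unknown correlation. **Any of three CDASI scores:** about 5% to 6%.
- **All three CDASI scores at n = 10:** about 72% to 77% power, reading CV 1.25 as damage and assuming the activity-damage correlation lies between −0.09 and 0.6.
- **All five items at n = 10:** about 37% to 74%, only if each has the CDASI activity effect.

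Confidence is high that the rule is missing and moderate for the ranges. It does not follow that the trial has an inflated error rate or too little power, because the plan does not commit to either rule. This is a cheap improvement.

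**What to change.** In Primary end-points, Statistical Methods and Sample Size Considerations, name one score as the sole primary endpoint: change in modified CDASI activity from baseline to 6 months, tested at two-sided 0.05, fixed before data are analysed. CDASI total would serve equally, since the plan sizes both identically. Move the other CDASI scores, CAT and the Physician's Global scores to secondary, report them with 95% confidence intervals, and state that none of them can establish primary success.

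This needs rewording only, with no change to visits, data collection or the stated 10 patients. Power stays at about 82% for a 50% fall if all ten are evaluable. The cost is that damage, CAT and Physician's Global lose primary status, so a significant result on one of them alone would no longer meet the primary endpoint.

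Keeping every item primary under an all-must-succeed rule is not recommended. It could need up to 15 evaluable patients, the top of planned enrolment, with no room for the discontinuations that Research Procedures allows.

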#### **2. Secondary end-points:**

a) Statistically significant change in **MDAAT** Score and **MMT-8** score

---

Protocol Version Date 7/30/14

- b) Statistically significant change in **Global Patient Score**, **Global Itch Score**, and/or the **Dermatology Life Quality Index scores** between baseline and 6 months.
- c) Safety and tolerability of H.P. Acthar gel based on frequency and types of adverse effects.
- d) median/mean change in glucocorticoid dose from initiation to completion of study.
- e) median/mean change in dose of systemic steroid-sparing immunosuppressive agents from initiation to completion of study.
- f) median/mean change in HbA1c

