***Inclusion Criteria:***

- Patients  $\geq$  18 years old with refractory cutaneous symptoms related to either classic dermatomyositis (CD), juvenile dermatomyositis (JD), or amyopathic dermatomyositis(AD). Diagnosis will be based on either Bohan and Peter criteria (CD and JD) or Sontheimer's criteria (AD) (4-7).
- Patients must have had a skin biopsy with histologic features consistent with dermatomyositis and current cutaneous manifestations consistent with dermatomyositis.
- Although not mandatory, patients with evidence of current or previous active myositis will be eligible for enrollment. Patients will be considered to have refractory disease if cutaneous manifestations exist despite treatment with steroids at least one steroid-sparing systemic treatment commonly found to be useful in patients with dermatomyositis. These may include azathioprine, cyclosporine, mycophenolate mofetil, IVIG, methotrexate, cyclophosphamide, chlorambucil, sirolimus, adalimumab, infliximab and rituximab.
- Use of topical medications and sunscreen currently and in past will be noted but not weighed for assessment of refractory cutaneous disease.

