10) Patients may continue their current immunosuppressive treatment regimens at the time of starting H.P. Acthar. If it is felt that patients should taper off of medications they will require a washout period:

- corticosteroids- 2 weeks
- methotrexate/azathioprine/mycophenolate/cyclosporine/sirolimus- 4 weeks
- adalimumab/infliximab/IVIG/chlorambucil/cyclophosphamide- 8 weeks
- rituximab- 6 months.

They will be instructed to continue topical medications, moisturizers, and sunscreen based on their current practice, which will be recorded at baseline and during subsequent visits.

11) All patients will receive 80 U (1 mL) of H.P. Acthar gel via subcutaneous injection twice weekly for 24 weeks (approximately 6 months).

12) Patients will require **follow-up visits in person at 1mo (+/- 5 days), 3mo (+/- 5 days), and 6mo (+/- 5 days)** after initiation of the H.P. Acthar, at which time examinations and clinical scoring tool assessments will be repeated.

13) If corticosteroids are continued in patients receiving H.P. Acthar gel they will be tapered at the primary investigator's discretion based on clinical evaluation at follow-up appointments.

14) H.P. Acthar will be discontinued in any given patient at the primary investigator's discretion if deemed necessary for the patient's overall health and well-being at any point during the study.

Serologic Studies	Baseline	6mo
CBC w/ diff	X	X
CMP	X	X
AM cortisol level	X	X
Creatine Kinase	X	X
Aldolase	X	X
LDH	X	X
C3	X	X
C4	X	X
HbA1c	X	X
Comprehensive myositis panel (ARUP labs)	X	

Length of above tests is that of a typical phlebotomy blood draw.

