### **Data Analysis**

Access to Data will be limited to the P.I., research coordinator, and research nurse. Approval from the IRB to allow access to data will be sought via an IRB amendment application if any additional research personnel are added to the study.

Confidentiality of patients will be protected by assigning numbers to patients and avoiding use of PHI. Results of the study will be reported in aggregate and anonymously

Statistical analyses will be conducted by the section of Biostatistics in the Quantitative Health Sciences department at the Cleveland Clinic using the methods described below:

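### Does the secondary endpoint on change in steroid-sparing dose need a stated rule for combining different drugs?

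*Combined protocol and SAP*

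**What the plan says.** Under Study End Points, secondary endpoint (e) is the "median/mean change in dose of systemic steroid-sparing immunosuppressive agents from initiation to completion of study". It does not list the agents, a dose unit or a method of combination. Endpoint (d) is the parallel item for glucocorticoids.

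The breadth of the drug class has to be taken from elsewhere. The Inclusion Criteria define refractory disease by earlier treatment and give examples: "These may include azathioprine, cyclosporine, mycophenolate mofetil, IVIG, methotrexate, cyclophosphamide, chlorambucil, sirolimus, adalimumab, infliximab and rituximab". That is eleven agents in an open list. Research Procedures item 10 then says "Patients may continue their current immunosuppressive treatment regimens at the time of starting H.P. Acthar", so different patients may be on different drugs. The same item adds "If it is felt that patients should taper off of medications they will require a washout period", with lengths of 4 weeks, 8 weeks or 6 months for the steroid-sparing drugs, depending on the agent. Item 13 covers on-study tapering of steroids: "If corticosteroids are continued in patients receiving H.P. Acthar gel they will be tapered", at the investigator's discretion.

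Statistical Methods assigns its tests of change to the scales: "Changes in scoring tool measures from baseline to six months will be calculated and compared using paired t-tests". The mixed models there are likewise for scores. Data Analysis gives the work to a biostatistics section and states that "Results of the study will be reported in aggregate and anonymously". The Sample section plans "approximately 10-15 patients with refractory cutaneous symptoms".

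**The concern.** A mean or median change in dose makes sense for one drug on one scale. Endpoint (e) names a class. The documents give no doses for these drugs, but a list that mixes small-molecule agents, biologics and IVIG is unlikely to share a common dose scale. Corticosteroids differ in this respect: the Exclusion criteria already express them in prednisone equivalents.

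Two things would be at stake. If raw doses were pooled, the drug with the largest numerical dose would dominate, and the mean and median could point in opposite directions. If doses were kept by agent, a sample of 10 to 15 would split into very small groups.

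There is also a question of timing. If the start of the interval were taken before the washout in item 10, a pre-treatment taper would be counted as a reduction on study. In an open-label study with all patients on the same drug, no control group would reveal this.

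**Working it through.** **The plan's own figure.** None is stated for (e). The main computed figure in Sample Size Considerations is 10 patients for a 50% decrease in CDASI activity or total score. Inputs: CV 0.6, within-person correlation 0.25, two-sided 0.05, 80% power, paired t-test on logs.

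- SD of the log difference = sqrt(2 × ln(1 + 0.6²) × (1 − 0.25)) = 0.679
- Effect = ln(0.5) = −0.693
- Noncentral t: N = 10, with power 0.82 at that size.

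The stated 10 is reproduced, and nothing in it uses (e).

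**Pooled reading.** All doses here are assumed, because the documents give none. Take ten patients: five halve an agent dosed at 1 unit, and five are on an agent dosed at *k* units. Three courses for the second group:

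| Second group | Pooled mean change | k = 1 | k = 10 | k = 100 | Mean percent change |
|---|---|---|---|---|---|
| raises dose 10% | (5 × (−0.5) + 5 × 0.1k)/10 = −0.25 + 0.05k | −0.20 | +0.25 | +4.75 | (5 × (−50) + 5 × 10)/10 = −20% |
| unchanged | (5 × (−0.5) + 0)/10 = −0.25 | −0.25 | −0.25 | −0.25 | (5 × (−50) + 0)/10 = −25% |
| halves dose | (5 × (−0.5) + 5 × (−0.5k))/10 = −0.25 − 0.25k | −0.50 | −2.75 | −25.25 | −50% |

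In the first row the mean crosses zero at k = 0.25/0.05 = 5. With a 6/4 split and the same 10% rise, the mean is −0.30 + 0.04k, which is +3.70 at k = 100. The median stays at −0.50 and the mean percent change is (6 × (−50) + 4 × 10)/10 = −26%. So mean and median can disagree in sign, but only because some doses go up. In the second and third rows the mean is negative at every k; only its size depends on units.

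**Do the documents provide for increases?** Item 10 speaks of continuing or tapering off, and item 13 of tapering corticosteroids. Neither provides for raising a steroid-sparing agent. The more likely pattern is many zeros with a few reductions.

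**Per-agent reading.** Assume one agent per patient and an even spread, neither of which is documented. Two agents in use give 10/2 to 15/2 = 5 to 7.5 patients each; three give 3.3 to 5; five give 2 to 3. These groups are small because the study is small.

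**Timing.** Outside endpoints (d) and (e), the protocol uses the word initiation only in item 12, where follow-up visits are counted from the start of H.P. Acthar. Read the same way, (e) starts at the first injection, after any washout. Under the other reading, a fully washed-out patient would enter at −100%. Compared with counting that patient as unchanged, this moves the mean percent change by 100/10 = 10 points among ten patients, or 100/15 = 6.7 points among fifteen.

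**Would a more formal summary gain much?** Counts of patients reduced, unchanged or increased do not depend on units. Their exact (Clopper-Pearson) 95% intervals are wide: 7/15 gives 21.3% to 73.4%, 5/10 gives 18.7% to 81.3%, and 3/6 gives 11.8% to 88.2%, or widths of about 52, 63 and 76 points. They would describe the sample without estimating anything precisely.

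**The case for a change.** The best case for amending the text is that the rule is missing and would be cheap to supply. No section says whether doses are pooled or separated, or how to treat patients on several agents or none. Writing the rule down beforehand would stop anyone choosing among mean or median, pooled or per agent, once the data are seen. It needs only the doses that (e) already calls for. The washout question adds to this, since a pre-study taper could be presented as a benefit of treatment.

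Much of this stands as description. The gap is real, and the start of the interval could be stated more plainly. But the harm depends on an analysis the plan does not state. Endpoint (e) never says that unlike doses will be added together, and a biostatistics section is unlikely to do so. The eleven agents define earlier treatment failure and are not a list of background therapy on study, so the actual mix may be narrow. Selective choice of summary matters most where a test or a decision follows, and here neither does: (a) and (b) are worded in terms of statistical significance, while (e) is not. Percent change from each patient's own starting dose, summarised across patients or by agent, also fits the commitment to aggregate reporting.

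**Conclusion.** No change to the plan is called for. Endpoint (e) leaves out a detail that competent analysts would fill by summarising per agent or relative to each patient's starting dose, and by counting from the first injection, as item 12 does. The prednisone-equivalent scale for (d) is already evident from the Exclusion criteria.

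The size is small. If raw doses were pooled, the magnitude would depend on units, but the sign could reverse only with on-study increases that the protocol does not provide for. The timing ambiguity is worth at most 6.7 to 10 points of mean percent change per fully washed-out patient, under the assumption that all 10 to 15 patients contribute. No test, decision, primary endpoint or sample-size figure depends on (e).

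This rests on two assumptions: that the analysts would not average unlike units, and that dose changes on study are mainly nil or downward. If many doses were raised and raw amounts were pooled, the result would mislead, but only in a descriptive secondary summary.
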